VII.E.6 *Provide a detailed description in sequential order of the study procedures following the consent process - DO NOT cut and paste from the Consent Document.*

Describe study populations separately if they will be participating in different procedures - include CONTROL population if applicable.

DESCRIBE:

- *What subjects will be asked to do/what happens in the study (in sequential order)*
- *The time period over which procedures will occur*
- *The time commitment for the subject for individual visits/procedures*
- *Long-term followup and how it occurs*

The approximate time required to complete all study activities (including consent) is 30-60 minutes.

Potential participants will answer pre-screening questions as listed on the Enrollment Checklist, these questions offer no inconvenience to the participant if after answering they are deemed ineligible to participate in the study. If they meet all inclusion and exclusion criteria they will be consented to participate. It is possible that additional information may come to light during study participation that indicates the individual does not meet the inclusion criteria, at which point their participation would end.

Following consent, post-screening questions will be completed to further verify a subject's eligibility in the study. These questions are asked post-consent because of the more involved nature of the materials, height and weight measurement, simple movement tasks to confirm eligibility. If the subject does not meet the post-screening question requirements, then their participation in the study will be terminated.

For group 2, personal and demographic factors collected in the Patient History Questionnaire will be used to characterize the study participants. We will collect multiple variables including age, gender, height, weight, and pathology to characterize the cohort. All patient health and demographic information will be self-reported by the patient while they are present in the study space, and no information will be collected from the patient's medical record at UIHC or APO.

All consent and data collection for Group 1 will be conducted at 21D EMRB. Group 2 consent and data collection will take place at either APO or 21D EMRB.

At time point 1, three scans using the Structure Core sensor will be obtained. Similarly, a digital caliper will be used to obtain three measures at pre-identified landmarks. A tape measure will be used to obtain limb circumference measures. Measurements that will be taken are 1) width of the metatarsal heads, 2) width of the calcaneus, 3) foot length, 4) foot height, 5) arch height, 6) medial-lateral width between ankle malleoli, 7) minimum circumference above the ankle malleoli, 8) maximum calf circumference, 9) medial-lateral width of the knee condyles 10) anterior-posterior width at mid patellar tendon, 11) distance from bottom of foot to tibial tubercle.

At time point 2 (same day as time point 1) the three scans using the Structure Core sensor will be obtained, precise calipers and a tape measure will again be used to obtain three measures at pre-identified landmarks.

The order of obtaining digital scans and physical measurements will be randomized across subjects to account for potential changes in limb volume during the course of testing.

All physical measurements will be stored for future data analysis. All limb scans will be stored for a 30 day period before being deleted; allowing time to extract digitally analyzed measurements. This set period for retention of the scans is mandatory for participation in this study. All personal identifiers will be kept separately from other data. Only a limited access master key document will link two data sets. Identifiable information will be kept in hard copy within locked file cabinets in restricted access areas or in a password protected database in restricted access of [name] lab in 21D EMRB. [name] has used these procedures for multiple funded grants.

VII.E.7 *Will you attempt to recontact subjects who are lost to follow-up?*
No - followup is not required in this study

VII.E.9 *Will subjects be provided any compensation for participating in this study?*
No

VIII. Risks

VIII.1 *What are the risks to subjects including*
- emotional or psychological
- financial

- *legal or social*
- *physical?*

The proposed study activities are considered no more than minimal risk which presumes that risks of the research are not greater, in and of themselves, than those ordinarily encountered in daily life. The risk benefit ratio of this proposed study is considered justifiable as it is relatively low risk and will provide valuable data, and lay an important knowledge framework for future AFO casting for patient populations.

The primary risks to study participants are loss of privacy and/or breach of confidentiality, which are known risks inherent to all research studies. To protect privacy and prevent breaches of confidentiality, we will use the minimal amount of identifiable information possible while still meeting the needs of the study. All study personnel will demonstrate knowledge of applicable regulations by completing courses of instruction through the CITI program. A code (e.g. P001) will be used to represent individuals on all study forms and files. Research team members will use standard practices to preserve the privacy of the participant as much as possible, such as refraining from discussing sensitive topics, referring to private health information or other personally identifiable information. Further, the scans of participants will be kept in a restricted access location.

Secondary risks to study participants are the possibility of injury or physical discomfort during implementation of study assessments. Subjects will be asked to stand on a platform without an AFO to conduct the 3D scanning methods.

VIII.2 *What have you done to minimize the risks?*

- *If applicable to this study ALSO include:*
 - *How you (members of your research team at Iowa) will monitor the safety of individual subjects.*
 - *Include a description of the availability of medical or psychological resources that subjects might require as a consequence of participating in this research and how referral will occur if necessary (e.g. availability of emergency medical care, psychological counseling, etc.)*

Study staff will speak with participants throughout the testing session to ensure safety and comfort. Risks to participants in the study are low since the protocol involves standing. The subject will be informed to indicate in person, or when not immediately evident, inform over the phone if any adverse event occurs. The event will be monitored and reported to the IRB in accordance with the governing policy and procedures. If an event occurs during the implementation of study procedures the most senior person locally available will be notified and a study team member can help facilitate securing appropriate medical or professional intervention if needed. In addition, a report of the adverse event will be provided to the IRB as required.

To minimize the risk of loss of confidentiality of data study activities will take place in the HPCO lab, away from other individuals. Collected data will be logged and tracked using a non-identifying participant code and time date code (alphanumeric subject ID (e.g. S001) and/or YYYYMMDD_TTTT) to protect participants identity. Study files will be carefully secured, paper copies through locked storage and electronic copies in a password-protected environment. Access to this information will be limited to properly trained individuals on the study team who require access.

VIII.3 *Does this study have a plan to have an individual or committee review combined data from all subjects on a periodic basis (such as summary or aggregate safety and/or efficacy data)?*

No

IX. Benefits

IX.1 *What are the direct benefits to the subject (do not include compensation or hypothesized results)?*

Participants will not receive direct benefit from participating.

IX.2 *What are the potential benefits to society in terms of knowledge to be gained as a result of this project?*

The results of this study will provide valuable data to for future clinical AFO casting optimization.

X. Privacy & Confidentiality

X.1 *What are you doing to protect the privacy interests of the subjects?*

The informed consent process and study procedures will be conducted in a private and secured laboratory space (21D EMRB or APO) to minimize the likelihood of individuals observing their participation or overhearing the participant's personal information. All data collection files and paperwork are coded at the time of collection (alphanumeric subject ID and/or YYYYMMDD_TTTT) ensuring there are no readily available links to the individual. Consent forms will be kept separate from data files. The participant video will be kept on a password restricted drive only accessible to authorized individuals. Further, we seek to collect no more data than necessary to answer the research question.

X.2 *Are you collecting the Social Security Number of any subjects for any purpose?*

No

X.4 *How will information/data be collected and stored for this study (check all that apply):*

- Paper/hard copy records (hard copy surveys, questionnaires, case report forms, pictures, etc.) - Data will be coded with links stored separately. Paper/hard copy study records will be stored in secured locations such as locked file cabinets in limited access locations within the Department of Physical Therapy and Rehabilitation Science ([name] Lab space in MEB and/or EMRB). Only coded data will be retained. Additionally, the previously described contact information will be retained separately.
- Electronic records (computer files, electronic databases, etc.) - Electronic records (computer files, etc.) will be stored on password protected computers and/or [name] RDSS network server drive. Access to the network requires both individual access to a University of Iowa computer using Healthcare ID and password, and permission to access the study folder which is controlled by [name] via HCIS. These steps serve to limit access to only study team members who can and need to have access. Only coded data will be retained. Additionally, the previously described contact information will be retained separately.
 - Name - [name]
 - Title - Director, Information Security
 - University Job Classification - Faculty/Staff

X.5 *Do the confidentiality protections indicated above allow only members of the research team to access the data/specimens?*

Yes

X.7 *Does your study meet the NIH criteria for a [Certificate of Confidentiality](#) or will you be applying for Certificate of Confidentiality?*

No

XI. Data Analysis

XI.1 *Describe the analysis methods you will use, including, if applicable, the variables you will analyze*

The data evaluation and statistical analysis for each aim is listed below:

Each 3D scan will be assessed by two raters to identify the digital landmarks of interest. The average of three values from time point 1 will be used to represent time point 1 and the average of three values at time point 2 will be averaged to represent time point two.

For Aim 1, the intraclass correlation coefficient (ICC) and minimal detectable change (MDC95) values will be calculated for each measure for comparisons between time point 1 and time point 2.

Measurements will be taken using the digital calipers or a tape measure at the identified landmarks of interest. The average of three values from time point 1 will be used to represent time point 1 and the average three measurements from time point 2 will be used to represent time point 2

For Aim 2, the ICC and MDC95 values will be calculated for each measure for comparisons between time point 1 and time point 2.

For Aim 3, concurrent validity will be determined by evaluating the correlation between measurements obtained using limb scanning and the calipers.

XI.2 *Provide the rationale or power analysis to support the number of subjects proposed to complete this study.*

The total number of participants proposed for each group in this study is consistent with prior studies by [name] related to AFO design. We are not aware of any existing data directly related to analyzing the repeatability and validity of 3D scanning for length and width measurement. Using the central limit theorem a total of 20 participants are required to get a stable estimate of the variability of a measure. It is for this reason we chose to enroll at least a total of 20 participants per group. 20 is the minimum target number, but due to a high volume of responses from the community more than 20 subjects can be enrolled.

XII. Future Research

XII.1 *Do you wish to keep any information about subjects involved with this research project so that members of the current research team may contact them in the future for your own research projects?*

Yes

XII.2 *Do you wish to keep any information about subjects involved with this research project so that [other researchers](#) may contact them for future research?*

No

XII.3 *List the data or information you will keep:*

First and Last name, Preferred phone number, Secondary phone number, Email address, Gender, Birth month, Birth

year, Interest in contact for future studies.

XII.4

Does this project involve storing any data, tissues or specimens for future research?

Yes – contribution for future use is mandatory for participation in the study

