A 3D representation of each participant's lower limb geometry will be obtained using a Structure Core scanner (Occipital, Inc.) which uses an infrared structured light projector to construct a 3D image of an object. The scanner is connected to an iPad; to operate the user rotates the iPad camera around the desired object. In seconds, the entire geometry is digitally reconstructed. Measurements will be evaluated using digital imaging analysis software (Standard Cyborg, Inc.). We will evaluate concurrent validity by directly comparing software-based measurements from limb scans, with direct measurements on the same individual collected using digital calipers. We will determine repeatability of each technique by conducting three identical limb scans and actual physical measurements at two time points on the same day in each individual, and then comparing the results between time points.

Validity and repeatability will be assessed using measurements at multiple locations on the lower leg. Limb measurements will include 1) width of the metatarsal heads, 2) width of the calcaneus, 3) foot length, 4) foot height, 5) arch height, 6) medial-lateral width between ankle malleoli, 7) minimum circumference above the ankle malleoli, 8) maximum calf circumference, 9) medial-lateral width of the knee condyles 10) anterior-posterior width at mid patellar tendon, 11) distance from bottom of foot to tibial tubercle.

Concurrent validity will be determined using the intra-class correlation coefficient and absolute error (root mean square error) for comparisons between measurements from limb scanning and the calipers. Reliability will be determined using the intra-class correlation coefficient and the minimal detectable change value for comparisons over time.

Study activities will either occur at American Prosthetics and Orthotics, or the Human Performance and Clinical Outcomes Laboratory (21D EMRB).

I.5 *Specify your research question(s), study aims or hypotheses (do not indicate "see protocol")*
AIM #1: To determine the test-retest and inter-rater reliability (Intraclass correlation coefficient) and minimal detectable change values for multiple measures of limb geometry as determined using 3D limb scanning and digital image analysis.

AIM #2: To determine the test-retest and inter-rater reliability (Intraclass correlation coefficient) and minimal detectable change values for multiple measures of limb geometry as determined using digital calipers or a tape measure.

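### Scan/physical order is randomised because limb volume may change, but no planned analysis uses it, so any common change could inflate the Aim 3 RMSE

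*Combined protocol and SAP*

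**What the plan says.** Under VII.E.6, each time point has three scans and three physical measures of each of 11 dimensions, by caliper or, for circumferences, by tape. The order of the two methods "will be randomized across subjects to account for potential changes in limb volume during the course of testing". For the second session the plan says "At time point 2 (same day as time point 1) the three scans using the Structure Core sensor will be obtained", again with three physical measures. It does not say whether a subject's order is kept or reversed there, whether allocation to the two orders is balanced, or whether each method's three readings are taken together or alternate with the other's.

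Aim 3 is described twice:
- Section I.4: "Concurrent validity will be determined using the intra-class correlation coefficient and absolute error (root mean square error" in parentheses, for scan against caliper.
- Section XI.1: "concurrent validity will be determined by evaluating the correlation between measurements obtained using limb scanning and the calipers". RMSE is not mentioned.

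XI.1 averages the three values within each time point and gives ICC and MDC95 between time points for Aims 1 and 2. Neither section has an order term, or says which time point feeds Aim 3.

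**The concern.** The plan names limb change during testing as a threat and randomises order because of it, then leaves order out of the analysis. For a mean difference that is largely harmless, since the change enters with opposite signs in the two orders and cancels in expectation. RMSE squares each difference, so the sign is lost and the change stays in.

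RMSE is the figure a reader would use to judge scanner error in millimetres. If limb volume does change between the scans and the physical measures, part of that figure is the limb and not the scanner. The randomised order would allow the common part to be estimated, but only if order is recorded and used. Change that reaches both methods equally between time points 1 and 2 cancels in the difference and is not at issue.

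**Working it through.** **Inputs from the documents.** Three readings per method, averaged within a time point (VII.E.6, XI.1); at least 20 subjects per group (XI.2), so 40 across two groups at the minimum; 60 expected in all (VI.1). XI.2 gives no SD, target ICC or precision, so its figure of 20 cannot be reproduced by formula; it is used here only as n. The documents give no bias, difference SD or limb change, so those sizes are assumed and expressed in difference SDs.

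**Model.** For one measure at one time point, scan minus physical = b + o·d + e, with b the method bias, o = +1 or −1 by order, d the common change between the two method means, and SD(e) = s.
- Expected mean difference = b + d × mean(o), which is b when order is balanced.
- Expected RMSE² = b² + s² + d² + 2·b·d × mean(o), which is b² + s² + d² when balanced.
- Ratio to the RMSE without change = sqrt(1 + d²/(b² + s²)).

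**Rise in RMSE, balanced order, s = 1:**

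| d | b = 0 | b = 0.5 | b = 1 |
|---|---|---|---|
| 0.25 | 1.000 to 1.031 (+3%) | 1.118 to 1.146 (+2.5%) | 1.414 to 1.436 (+1.6%) |
| 0.5 | 1.000 to 1.118 (+12%) | 1.118 to 1.225 (+9.5%) | 1.414 to 1.500 (+6%) |
| 1.0 | 1.000 to 1.414 (+41%) | 1.118 to 1.500 (+34%) | 1.414 to 1.732 (+22.5%) |

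If s were 3 mm, the b = 0 column would run from 3.00 mm to 3.09, 3.35 and 4.24 mm for d of 0.75, 1.5 and 3 mm.

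**Simulation check** (40,000 samples, n = 20, balanced, b = 0; d = 0, 0.25, 0.5, 1.0). Unadjusted RMSE was 0.999, 1.029, 1.118 and 1.415. With order in the model it was 0.999, 0.998, 1.000 and 1.001. The mean difference stayed within 0.002 of b.

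**Blocks or alternation.** Take six equally spaced readings and linear drift. In blocks, the two method means fall at positions 2 and 5, three steps apart. Alternating (1, 3, 5 against 2, 4, 6), they fall at 3 and 4, one step apart. So d falls to one third and d² to one ninth, and the b = 0 rises become sqrt(1 + d²/9) = +0.3%, +1.4% and +5.4%.

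**Correlation.** With between-subject SD S, error split equally between methods and d split about the midpoint, r = (S² − d²/4)/(S² + s²/2 + d²/4). At S = 25 mm and s = 3 mm (assumed), d = 0, 1, 2 and 3 mm gives 625/629.5, 624.75/629.75, 624/630.5 and 622.75/631.75, or 0.993, 0.992, 0.990 and 0.986. Where subjects differ little the movement is larger: at S = 2s, d = 0.5s takes r from 4/4.5 = 0.889 to 3.9375/4.5625 = 0.863.

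**Precision of the order effect.** The 95% half-width is t(0.975, n−2) × s/sqrt(n): 2.101/4.472 = 0.47s at n = 20, 0.32s at n = 40 and 0.26s at n = 60. At n = 20, a d of one third of s would be told from zero in about 30% of samples.

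**Limits of the term.** If the change varies between subjects (mean 0.5, SD 0.25), RMSE is sqrt(1 + 0.25 + 0.0625) = 1.15 without the term and sqrt(1 + 0.0625) = 1.03 with it. Only the common part is removed.

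**The case against.** The strongest reply is that the design already does what it set out to do. Randomising order protects the expected mean difference; a fixed order would have put the change straight into the bias. XI.1, the data analysis section, names only a correlation, and RMSE appears only in the I.4 summary. The time for change is short: "The approximate time required to complete all study activities (including consent) is 30-60 minutes", and of a scan "In seconds, the entire geometry is digitally reconstructed". Circumferences, the measures most plainly tied to limb volume, are 2 of the 11; that is a judgement, and soft-tissue widths may also respond. What remains makes agreement look worse on average, so it does not flatter the scanner. An order term at n = 20 is imprecise and cannot be separated from carryover between methods.

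Most of this stands. It limits the size and importance of the point but does not answer it: randomisation protects the mean and not the RMSE, and the plan names RMSE.

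A reader might also infer that limb change does inflate the reported error, perhaps by the larger percentages above. The documents do not support that. They call the change potential, give no size, and do not say the readings are taken in blocks. Nor do they support conclusions about results averaged over the two time points, because XI.1 averages only within each time point.

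**Conclusion.** The point holds in conditional form, as a low-cost improvement. If there is common change between the scans and the physical measures of a time point, randomised order does not keep it out of RMSE; under balanced order RMSE² rises by d² in expectation. The 3%, 12% and 41% figures rest on assumed d of 0.25, 0.5 and 1.0 difference SDs, zero bias and blocked readings; bias or alternation makes them smaller. The true size is unknown and probably small.

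The rise is an expectation. With unbalanced order and non-zero bias, the cross term can raise or lower RMSE in one sample. Under simple randomisation at n = 20, a split of 14/6 or worse has probability 0.115, and 14/6 leaves 0.4d in the raw mean difference.

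The choice between I.4 and XI.1 matters more than the order term: a correlation alone does not measure agreement, because a constant offset leaves it unchanged.

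**What to change.** 1. Reconcile I.4 and XI.1 so that Aim 3 reports RMSE and mean bias, with any correlation or ICC alongside.
2. Record the scan/physical order for each subject and time point. State whether readings are blocked or alternated, whether allocation is balanced, and whether order is kept or reversed at time point 2. Existing records may not suffice: VIII.2 says "Collected data will be logged and tracked using a non-identifying participant code and time date code", but offers the two codes as and/or alternatives, and VII.E.6 deletes scans after 30 days.
3. Add to XI.1:

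> For Aim 3, the scan-minus-physical difference for each measure at each time point will be modelled with measurement order (+1/−1) as a fixed effect, adjusting for group. We will report the order-balanced mean bias, the order effect with 95% CI, the residual SD, and RMSE both unadjusted and adjusted as sqrt(bias² + residual variance × (n−1)/n).

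Form both RMSE values within group, using that group's bias and n; otherwise the adjusted figure would also drop any difference in bias between groups. Since "Each 3D scan will be assessed by two raters to identify the digital landmarks of interest", state how the two raters' values enter the difference.

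**Cost.** One recorded variable per time point, one degree of freedom, and 11 × 2 = 22 short models; no added measurements or visits. Report the order effect as an estimate, not as a test for dropping the term: it is known only to about ±0.47 difference SD at n = 20 (±0.32 at n = 40), removes only change common to all subjects, and cannot be told from carryover.

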AIM #3: Determine the concurrent validity of measures obtained using 3D limb scanning and digital caliper-based measurements or a tape measure.

1.6

Background and significance and/or Preliminary studies related to this project. (do not indicate "see protocol")

Ankle foot orthoses (AFOs) are braces that are used to maintain or restore mobility for individuals with lower limb pathology. A well-fitting device is essential for proper comfort and function. Unfortunately, the fitting process has seen little advancement in recent years. It is common for an orthotist to take a cast of a patient's lower leg and foot to create the geometry for the AFO. Due to the craft based fitting process, each cast and device is unique, and it is difficult to objectively refine or improve the fitting process.

3D limb scanning is being implemented in the clinical setting for calculating residual limb volume [1]. Similar affordable scanning technology has been tested for the reliability and validity of its measurements for obtaining residual limb volume, using the gold standard of water displacement as comparison [2]. A study comparing 3D laser scanning for measuring limb volume against the water displacement method suggests that scanning can provide accurate and reproducible measurements [3].

Custom orthotic devices manufactured with 3D scanning and rapid prototyping have been found to be a better geometrical fit, and have similar function, when tested against prefabricated orthotics [4]. Using 3D scanning methods for casting can be more economical and time efficient [4,5]. Additive manufacturing (AM) is a promising technique to mass produce custom AFOs; however, there is little data to quantitatively and qualitatively compare the AM approach to traditional casting methods [5]. There is a clear lack of technological data, as well as clinical acceptance, to the AM method of producing a custom AFO [6]. The ability to use AM approaches to consistently provide quality fitting AFOs is dependent on the ability to obtain accurate and reliable limb geometry using 3D limb scanning. Therefore, in this study we seek to evaluate the repeatability and validity of multiple lower limb measurements obtained using low-cost 3D limb scanning technology.

1.7

Literature cited / references (if attaching a grant or protocol enter N/A).

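### XI.1 judges Aim 3 by an unspecified correlation and omits the RMSE given in I.4; a Pearson or consistency-type coefficient would hide a constant scanner offset

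*Combined protocol and SAP*

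**What the plan says.** XI.1 opens with "The data evaluation and statistical analysis for each aim is listed below". For Aims 1 and 2 it names the ICC and MDC95, in each case comparing time point 1 with time point 2. For Aim 3 it offers only this: "For Aim 3, concurrent validity will be determined by evaluating the correlation between measurements obtained using limb scanning and the calipers". It gives no type of correlation, no measure of absolute error and no threshold for calling the scanner valid.

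I.4, also current text, treats the same comparison differently: "Concurrent validity will be determined using the intra-class correlation coefficient and absolute error (root mean square error"). It does not state the form of ICC either.

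Three other places bear on the point:

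- I.5 words the aim as "Determine the concurrent validity of measures obtained using 3D limb scanning and digital caliper-based measurements or a tape measure", and VII.E.6 adds "A tape measure will be used to obtain limb circumference measures". Two of the 11 measures (minimum circumference above the malleoli and maximum calf circumference) therefore have the tape as comparator. The Aim 3 sentence in XI.1 mentions calipers only.
- XI.1 also states "Each 3D scan will be assessed by two raters to identify the digital landmarks of interest" and averages three values at each of two time points. It does not say whose scan values, or which time point, enter Aim 3.
- I.6 says that supplying well-fitting AFOs by additive manufacturing is "dependent on the ability to obtain accurate and reliable limb geometry using 3D limb scanning".

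**The concern.** Validity against a physical measurement is a question of agreement: does the scanner return the same number of millimetres? A correlation asks something else, namely whether limbs that measure larger by one method also measure larger by the other. Random error lowers a correlation, so the statistic is not useless. Under Pearson or a consistency ICC, however, a fixed systematic error leaves no trace.

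Nothing else in XI.1 would catch such an error. Aims 1 and 2 compare time points within one method, so a constant offset cancels there too. Accuracy, which I.6 makes a precondition for the intended use, rests on Aim 3 alone. Because no validity threshold is set, the reader will judge the scanner by whichever statistic is reported. If XI.1 is followed as written with an ordinary correlation, a scanner that is consistently several millimetres out could be reported as valid with a coefficient near 1.

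**Working it through.** **Inputs.** XI.2 gives a minimum of 20 participants per group. The documents give no between-subject SD, error SD or offset, so the values below are assumptions chosen to show a range.

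**Model.** For one measure, physical = T + e1 and scan = T + b + e2. Here *sb* is the SD of T between subjects, *se* is the error SD of each method's averaged value, and *b* is the constant offset. Then:

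- Pearson r = consistency ICC = sb² / (sb² + se²), which does not contain b
- absolute-agreement ICC = sb² / (sb² + se² + b²/2)
- RMSE = √(b² + 2se²)

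That r does not depend on b is algebraic and holds for any SDs.

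**Results.**

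| sb (mm) | se (mm) | b (mm) | r | Absolute-agreement ICC | RMSE (mm) |
|---|---|---|---|---|---|
| 6 | 1 | 0 | 36/37 = 0.973 | 36/37 = 0.973 | √2 = 1.41 |
| 6 | 1 | 1 | 0.973 | 36/37.5 = 0.960 | √3 = 1.73 |
| 6 | 1 | 2 | 0.973 | 36/39 = 0.923 | √6 = 2.45 |
| 6 | 1 | 5 | 0.973 | 36/49.5 = 0.727 | √27 = 5.20 |
| 6 | 3 | 0 | 36/45 = 0.800 | 36/45 = 0.800 | √18 = 4.24 |
| 6 | 3 | 5 | 0.800 | 36/57.5 = 0.626 | √43 = 6.56 |
| 20 | 1 | 5 | 400/401 = 0.998 | 400/413.5 = 0.967 | √27 = 5.20 |

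**Check by simulation.** With n = 20, sb = 10, se = 1 and 4,000 replicates, a 10 mm offset gave mean r 0.990, consistency ICC 0.989, absolute-agreement ICC 0.647 and RMSE 10.08 mm. The closed forms give 0.990, 0.990, 0.662 and 10.10.

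**What each statistic can and cannot show.**

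- r does respond to random error: it is 0.94, 0.80 and 0.50 at se/sb of 0.25, 0.5 and 1. Only systematic error is hidden.
- The absolute-agreement ICC sees the offset, but weakly when subjects differ widely. At sb = 20 mm a 5 mm offset still gives 0.967.
- RMSE sees the offset but mixes it with random error. An RMSE of 5.20 mm arises from b = 5 with se = 1, or from b = 0 with se = 5.20/√2 = 3.7.
- The mean difference and limits of agreement (b ± 1.96 × √2 × se) separate these two cases. The first gives 5 ± 2.8, or 2.2 to 7.8 mm. The second gives 0 ± 10.2, or −10.2 to 10.2 mm.

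**Precision available.** The 95% CI half-width for the mean difference in one group of 20 is t(0.975, 19) × √2 × se / √20. With t = 2.093 this is 0.66, 1.32 and 1.99 mm for se = 1, 2 and 3 mm. Under these assumptions the planned minimum sample estimates an offset to within about 2 mm or better.

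**The case against.** The strongest reply is that I.4 and XI.1 belong to one document. VII.B.11 says there is no separate protocol, so the two should be read together. On that reading, correlation in XI.1 is shorthand for the intraclass correlation named elsewhere, RMSE is already planned in I.4, and the gap is one omitted term. An absolute-agreement ICC would show an offset, so it is too broad to say that no correlation can. The study is one of estimation without a decision rule. VII.B.32 says a clinician sets the final geometry in current care. VII.E.6 keeps the physical measurements and allows time to extract scan measurements before the scans are deleted, so RMSE or a mean difference could be calculated later. All the millimetre inputs are assumed.

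Much of this is fair, and it limits the point. On the ICC, XI.1 is ambiguous and does not flatly contradict I.4. The plan as a whole does not lack an absolute-error measure, and no information is lost for good. The tape-measure omission is a matter of wording, since other sections make the comparator clear. The assumed values say nothing about how large this scanner's offset is.

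It does not dispose of the concern. XI.1 presents itself as the list of analyses, names the ICC for two aims and not for the third, and leaves out RMSE on any reading. Reading it as ICC does not settle the matter, because the form is unstated and a consistency ICC misses an offset exactly as Pearson does. That a better statistic could be computed later does not commit anyone to report it. Limits of agreement and a CI for the mean difference do go beyond bare alignment with I.4. They are recommended because RMSE and ICC do not isolate the offset.

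**Conclusion.** The concern holds. XI.1 and I.4 specify different analyses for Aim 3. The one in XI.1, taken as an ordinary or consistency-type correlation, cannot detect a constant scanner error in the only aim that addresses accuracy. That conclusion needs no numerical assumption. The size is illustrative only: with an assumed between-subject SD of 6 mm and error SD of 1 mm, a 5 mm offset would be reported as r = 0.97, against an absolute-agreement ICC of 0.73 and an RMSE of 5.2 mm. Aligning XI.1 with I.4 removes most of the problem but not all of it, because the ICC form is open and RMSE does not separate bias from random error. This is a specification fault that should be corrected before the data are analysed; it does not threaten data collection.

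**What to change.** Make XI.1 and I.4 agree, and replace the Aim 3 sentence in XI.1 with wording such as:

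> For each of the 11 measures we will report the mean scan-minus-physical difference with 95% CI and 95% limits of agreement, the RMSE, and the absolute-agreement ICC with 95% CI. The comparator is the caliper, or the tape measure for the two circumferences. Values are the means of three at time point 1, with scan values from one rater named in advance; time point 2 and the second rater are reported as a check. Correlation alone will not be taken as evidence of validity.

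If the team prefers time point 2, or the mean of both raters, that is acceptable provided it is stated in advance. Adjustment for the randomised order of methods is optional.

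The cost is a change of wording and a few lines of analysis code, using measurements already planned. The results may look less favourable than a correlation close to 1.
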